The description of adverse events in the manuscripts used for the literature review is not uniform; some authors describe the adverse events in detail, while other do not (see the tables in **Appendix B**, listing all adverse events mentioned in the control articles). In light of this limitation, the Company used the safety data provided in Table 7 of the FDA's Executive Summary for DDD patients (n=1,350; complications=921; re-operation=814). The relevant section (*i.e.*, DDD patients) of the said table is presented below:

ADEVERSE EVENT	RATE
Screw Malposition	0.5%
Screw Loosening	0.4%
Rod/Plate/Screw Breakage	1.3%
Construct Disassembly	0.1%
Bone Fracture	-
Graft Settling/Displacement	0.1%
Pseudoarthrosis	5.9%
Bleeding/Vascular Injury	0.7%
Neurologic Injury	0.8%
Nerve Root injury	0.3%
Spinal Cord Injury	0.0%
Back/Leg Pain (Radiculopathy)	0.7%
Dural Tear/CSF Leak	1.0%
Wound problems (Hematoma/Seroma)	0.3%
Infection/Sepsis	3.9%
Superficial	2.6%
Deep	0.9%
Skin Irritation	0.3%
Cardiac	0.2%
Respiratory	0.4%
Gastrointestinal	0.3%
Urologic/Reproductive	0.1%
Reoperation/Revision	10.9%
Removal of Hardware	5.5%

It is not possible to simply sum the event rates for each adverse event to establish a control adverse event rate for several reasons. The table above does not specify the adverse event severity or device relatedness. Further, the same type of adverse event, such as skin irritation, may be categorized with various degrees of severity depending on the actions taken to resolve

the event. In addition, it is possible that several adverse events occurred in the same patient, which means summing the rates would lead to an erroneously high adverse event rate.

Therefore, the Company believes that a conservative estimate of relevant adverse events can be obtained by summing all device-related serious adverse events, all reoperations/revisions and all neurological injuries.

Therefore, the rate of failure of devices in the control group for safety reasons is 13.5% which includes all device-related serious adverse events (including screw loosening, implant breakage and construct disassembly), reoperations/revisions and neurologic injuries.

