The **motor evaluation** measures the muscle strength in major muscle groups (Gluteus Maximus (hip extension); Iliopsoa (hip flexion); Quadriceps (knee extension); Hamstrings (knee flexion); Anterior Tibial Group (ankle dorsiflexion); Extensor Hallucis Longus (great toe extension); Posterior Tibial (ankle plantar flexion/eversion); and Flexor Halluces (great toe flection)). Muscle strength is evaluated on a 6-point scale ranging from 0 to 5 according to the following key

describing the ability of the patient to move the lower extremities against resistance provided by the examiner:

- ▶ 0 no movement;
- ▶ 1- muscle contraction;
- > 2 lateral movement;
- ➤ 3 against gravity;
- ➤ 4 against moderate resistance;
- \blacktriangleright 5 against full resistance.

Light-touch will test **sensation** for all lumbar and sacral dermatomes in comparison to the contralateral site. The sensation shall be graded as equivalent (normal), impaired, absent, as compared to the contralateral side.

Reflexes (Patella and Achilles) are evaluated according to Bate's Reflex Scale (a 5-point scale ranging from 0 to 4) as follows:

- > 0 − no reflex;
- > 1 somewhat diminished, low normal;
- \triangleright 2 average, normal reflex;
- > 3 brisker than average;
- ➤ 4 very brisk, hyperactive.

Straight leg raising is assessed by measurement of the degree of movement required to reproduce symptoms. A positive test is considered when the patient reports worsening of pain between 30 and 70 degrees of hip passive flexion while knee is extended.

Tenderness will be evaluated by palpation of the lower spine area – lumbar paraspinal region, lumber spinous process, sacroiliac joint, and sciatic notch. Tenderness shall be graded as negative or positive (*i.e.*, palpation provokes painful sensation).

 Patient Success –

Individual patient success with respect to *safety* is defined as:

- No worsening in neurological status (motor, sensory, reflex, straight leg raising, and tenderness assessments) and no new permanent neurological deficits present for at least 2 successive visits at or beyond 6 months (out to 24 months);
- Absence of device-related serious adverse events through 24 months;
- Absence of subsequent surgical interventions at the index level through 24 months.

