5.12 STUDY SUCCESS CRITERIA

The results of the study at 12 months and 24 months postoperatively for all participating subjects will be evaluated, with reference to the reported results from the

literature, as summarized in **Section 5.2.1**. In addition, assessment of success rate will be conducted at each time point, as applicable.

In addition to evaluating individual patient success as the primary composite endpoint, each element of the composite will be evaluated individually as secondary endpoints, as described below.

Fusion – Success for the fusion outcome measure will be defined as two year fusion rate comparable to the two and one year fusion rates presented in the literature. The pooled results of the Company literature research (for patients with DDD treated with pedicle screws with PLIF/ALIF/TLIF and/or PLF), as presented in **Section 5.2.1**, demonstrated at 12 and 24 months postoperatively fusion rates in the different studies ranging from 77% to 97%.

As discussed in **Section 5.2.1.A**, the weighted average for the fusion rate of the ten articles is 87.79%. Based on the literature, we believe our fusion rate will be 88%.

The assumed fusion rate of 88% has a 95% confidence interval of $\pm 6.4\%$ for 100 patients. Notably, the lower bound of this confidence interval, 81.6%, is within the range of the fusion rates reported in the selected literature.

Safety – Success with regard to safety outcome measure is defined as no worsening in neurological status (motor, sensory, reflex, straight leg raising, and tenderness assessments) and no new permanent neurological deficits (present for at least 2 successive visits at or beyond 6 months), absence of device-related serious adverse events, and absence subsequent surgical interventions at the index level, through 24 months, comparable to neurological deficit, device-related serious adverse events, and subsequent surgical interventions rates presented in the literature.

Based on the literature review in FDA's Executive Summary, the rate of these events in the literature control is 13.5%.

Therefore, the Company estimates that the adverse event rate for these events will be 13.5%. With a sample size of 100 patients, this adverse event rate has a 95% confidence interval of $\pm 6.7\%$.

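### The 13.5% literature safety rate is not like-for-like with the trial's safety endpoint and should not be presented as the rate of the same events

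*Combined protocol and SAP*

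**What the plan says.** Section 5.2.1 D takes event rates for DDD patients from a table in an FDA summary. It warns against adding up all the rows: "The table above does not specify the adverse event severity or device relatedness", and one patient may have had several events. It then adds selected rows, calls the result conservative, and concludes that "the rate of failure of devices in the control group for safety reasons is 13.5% which includes all device-related serious adverse events". It names loosening, breakage and disassembly as those events and adds reoperations/revisions and neurologic injuries.

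Patient-level safety success in the trial (5.10.3, repeated in 5.12) has three parts:
- no worsening on motor, sensory, reflex, straight leg raising or tenderness assessment, and no new permanent deficit;
- no device-related serious adverse event through 24 months;
- "Absence of subsequent surgical interventions at the index level through 24 months".

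Section 5.12 (Safety) asks that the rates of these failures be comparable to the literature, with no margin or test. It states that "the rate of these events in the literature control is 13.5" per cent, and takes 13.5% as the expected trial rate, with a 95% confidence interval of ±6.7 points for 100 patients.

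**The concern.** The device-related and serious label has no support in a source that, on the plan's own account, records neither property. Section 5.12 then drops the caveat and treats the sum as the rate of the trial's own endpoint. Safety has its own stated success criterion, and 13.5% is its only combined benchmark and its planning rate. If the two rates count different things, an observed rate near or below 13.5% cannot be read as showing comparability on the same events, and a rate above it cannot be read as showing a deficit.

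**Working it through.** **Inputs**, all from the table in 5.2.1 D, in per cent: "Screw Loosening 0.4"; "Rod/Plate/Screw Breakage 1.3"; "Construct Disassembly 0.1"; neurologic injury 0.8; reoperation/revision 10.9.

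**1. Reproducing the plan's figures.** 0.4 + 1.3 + 0.1 + 0.8 + 10.9 = 13.5. Adding a neighbouring row breaks the match: malposition (0.5) gives 14.0, nerve root injury (0.3) gives 13.8, removal of hardware (5.5) gives 19.0. So the three implant rows enter whole, whatever the severity of the events in them. The half-width is 1.96 × √(0.135 × 0.865 / 100) = 0.067, the stated 6.7 points.

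**2. What the sum is made of.** Implant events: 0.4 + 1.3 + 0.1 = 1.8 points, 1.8/13.5 = 13%. Reoperations/revisions: 10.9/13.5 = 81%. Neurologic injury: 0.8/13.5 = 6%. The unstated spinal level therefore matters far more than the unstated severity.

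**3. The two definitions side by side.**

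| Component | Literature 13.5% | Trial failure (5.10.3) | Effect of the mismatch |
|---|---|---|---|
| Implant and device events | Three failure modes; severity and relatedness unknown | Serious and device-related, any type | Both ways: the literature side may include non-serious events; the trial side is not limited to three modes |
| Surgery | All reoperations/revisions; level not stated | Index level only | Raises the literature side if off-level surgery is included |
| Neurology | One row of reported injury | Worsening on five assessments, or a new permanent deficit | Covers more signs, so raises the trial side; the two-successive-visit condition narrows at least part of it |

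Section 5.10.3 also lists injections, stimulators and rhizotomies among subsequent interventions. Whether they count as surgical failures is unclear, since the table in 5.14.4.2 codes them separately. If they count, the trial rate rises.

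**4. Illustration of size.** Let *f* be the share of reoperations at the index level and *s* the share of implant events that were serious and device-related. The documents give neither; both are assumptions. Matching part = 10.9*f* + 1.8*s* + 0.8 (per cent):

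| *f* | *s* = 1 | *s* = 0.5 | *s* = 0 |
|---|---|---|---|
| 1.00 | 13.50 | 12.60 | 11.70 |
| 0.90 | 12.41 | 11.51 | 10.61 |
| 0.75 | 10.78 | 9.88 | 8.98 |
| 0.50 | 8.05 | 7.15 | 6.25 |

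The range is about 6.3% to 13.5%. At its far end the gap is 13.5 − 6.25 = 7.25 points, slightly more than the 6.7-point half-width. The opposing effects, from the wider neurological examination and from serious device-related events of other types, cannot be quantified from the documents.

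**5. A sum is not a patient rate.** If every implant and neurologic event occurred in a patient who also had a reoperation, the per-patient rate would be 10.9%, not 13.5%, even with no restriction by level. The source also gives different counts (n = 1,350; complications 921; re-operation 814), so the rows may not share a denominator.

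**The case against.** The plan discloses the limits of the table in 5.2.1 D. The analysis is declared descriptive (5.2), safety needs only to be comparable, and study success rests on a 41% composite rate (end of 5.12) that does not use 13.5%. The wording in 5.12 also names the three kinds of event separately, so a comparison by component may have been intended. All of this limits the consequence. It does not cure the label in 5.2.1 D or the equation in 5.12, where the caveat is gone.

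A reader might go further and infer that the comparison is biased in favour of the device. The documents do not support that. The source is silent on reoperation level; silence does not show that adjacent-level surgery is in the 10.9%. The trial's neurological component, its inclusion of device-related serious events of any type, and possibly its list of interventions push the other way. The illustrative range also includes 13.5% itself.

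A reader might also fear that implant failures or adjacent-level surgery would be hidden. That does not follow either. Adverse events are to be listed individually and reported by type, seriousness and relatedness (5.13.4), with separate rows for implant breakage and loosening and for index and adjacent-level reoperation (5.14.4.2). An independent events committee reviews them.

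**Conclusion.** The point holds in limited form. The 13.5% is reproduced exactly, but it is a sum of row rates for events that differ from the protocol's safety failures, and calling it the rate of those events is wrong as written. How much of it matches the trial definition is unknown. On the assumed shares it is about 6.3% to 13.5%, before allowing for the trial's wider neurological definition. The net direction of bias is undetermined, so the description of 13.5% as conservative is not shown. To call the whole safety comparison invalid would go too far, given a descriptive analysis, itemised adverse event reporting and a study-level criterion that does not depend on this figure.

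**What to change.** 1. In 5.2.1 D, replace the device-related serious label with *implant events of unspecified severity and relatedness*, and state that the level of the reoperations is not given.
2. In 5.12 (Safety), keep the protocol safety criterion for the composite, but stop presenting 13.5% as its literature or expected rate.
3. For the literature comparison, report Implant Loosening, Device Breakage, Construct Disassembly, Neurologic Injury and Reoperation/Revision (all lumbar levels, with index level shown separately), regardless of seriousness or relatedness. Give each as a per-subject rate with a 95% confidence interval, beside its own literature row.
4. Do not set one per-subject any-event rate against the summed 13.5% as if the two were matched.
5. Confirm that the roughly 45 patients from the ongoing OUS study (5.13.1) have adverse events coded to the same terms and levels; the documents do not say so.

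The terms are already in 5.13.4 and the levels in 5.14.4.2, so no new data are needed for the 55 IDE patients. The cost is wording, one extra table and the check on OUS coding. The safety comparison may look slightly less favourable.

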Several of the studies evaluated fusion using tools and definitions less rigorous than those suggested for the proposed IDE study (*e.g.*, without flexion-extension radiographs, and thus with no motion assessment). Therefore, the reported fusion rates of those articles may be regarded as worst case for the purpose of comparison. On the other hand, one study (*Anjarwalla*) used thin cut CT to evaluate fusion, which is expected to yield a slightly lower fusion rate. Although the proposed study uses radiographs to assess fusion, both studies use x-rays to assess fusion. Therefore, the slight difference in imaging modalities does not preclude using the results of the study when determining the control fusion rate.

Please note, that the ten studies utilized autogenous bone graft (mainly iliac crest bone graft), which is associated with higher fusion rates than allograft.

Overall, the compilation of these ten articles, reporting fusion results for a total of 556 DDD patients, provides for reliable control group for comparison of fusion rate. It is emphasized that all of the mentioned studies were regarded as appropriate for the review of DDD patients in the FDA Executive Summary, and thus are reported in Table 6 of the said document.

Seven of the ten studies report fusion rates at two years, while two studies (*Christensen* and *Nrayan*) reports rates at one year. One study (*Christensen* II) reports fusion rate at both one and two years. Slightly higher fusion rates are expected at two years as compared to one year. As the fusion rate of the subject device is assessed at one year, it is either analogous or worst-case compared to the literature control. Therefore, despite differences in time points, a valid comparison can be made.

Fusion success rates reported in the ten manuscripts, and calculated weighted average of values, are presented in the tables below. The weighting factor is the number of patients in each study.

	Single Level	Double Level	Procedure	Diagnosis	Cohort Size	Fusi N _{fused} /I		Fusion Rate [%]
Fritzell 2002 (Arm I)	N ₂₄ =43	N ₂₄ =21	ALIF or PLIF + PLF + PSS	DDD	N ₂₄ =64	58	64	91 2 years
Fritzell 2002 (Arm II)	N ₂₄ =35	N ₂₄ =27	PSF + PSS	DDD	N ₂₄ =62	54	62	87 2 years
Zigler 2007	N ₂₄ =69	-	ALIF + PLF + PSS	DDD	N ₂₄ =69	67	69	97 2 years
Anjarwalla 2006	N ₂₄ =14	N ₂₄ =10	ALIF + PLF + PSS	DDD	N ₂₄ =24	21	24	88 [§] 2 years

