5.10.3 SAFETY EVALUATION

The safety evaluation will be based on the reported complications and adverse events (AEs), including subsequent surgical interventions and neurological status. Complications/Aes shall be evaluated at each follow-up session, as well as throughout the study.

1. Complications/Adverse Events

All the reported complications/adverse events, whether device-related or not, including "anticipated" complications, will be recorded.

Refer to Section 5.14.4.1 for adverse event definitions.

2. Subsequent Surgical Intervention

Information regarding subsequent interventions will include category of procedure, as defined below, the reason for the procedure and whether or not the subsequent procedure constitutes a study failure.

Subsequent surgical intervention will be categorized as a revision, removal, reoperation, or supplemental fixation at the affected level/s, as defined hereinafter.

Revision – a second procedure that adjusts or in any way modifies or removes *part* of the original implant configuration, with or without replacement of a component. A revision may also include adjusting the position of the original configuration.

Removal - a procedure where *all* of the original system configuration are removed with or without replacement.

Reoperation – any surgical procedure at the involved level/s that is not removal, modification, or addition of any components to the system (e.g., irrigation and debridement).

Supplemental Fixation – a procedure in which additional instrumentation not under study in the Protocol is implanted.

Subsequent interventions in spinal studies include epidural injections, the implantation of spinal stimulators, and rhizotomies.

3. Neurological Status

A neurological examination will be performed preoperatively and at discharge, and at all postoperatively visits, to assess neurological status. The evaluation of neurological status will include motor, sensory, reflex, straight leg raising, and tenderness assessments, as hereby described. Each component shall be assessed separately on each anatomical side (left, right). The following paragraphs describe the five neurological examinations.

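### The 13.5% safety reference is the no-overlap maximum of five event rates, not a conservative figure, and the fusion reference is defended by a one-year assessment that contradicts the 24-month endpoint

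*Combined protocol and SAP*

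**What the plan says.** **Safety.** Section 5.2.1 part D takes an adverse event table from an FDA summary, with the note "n=1,350; complications=921; re-operation=814". It explains that the rates cannot simply be added, partly because one patient may have several events, "which means summing the rates would lead to an erroneously high adverse event rate". It then says that "a conservative estimate of relevant adverse events can be obtained by summing all device-related serious adverse events, all reoperations/revisions and all neurological injuries", and arrives at 13.5%. Section 5.12 adopts this: "the rate of these events in the literature control is 13.5" per cent. It defines safety success as being comparable to the literature and gives no margin.

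**Fusion time point.** Sections 5.1.1, 5.10.1 and 5.12 set fusion at 24 months, and section 5.7 places the primary analyses there. Section 5.2.1 part A nevertheless defends mixing one- and two-year literature rates as follows: "As the fusion rate of the subject device is assessed at one year, it is either analogous or worst-case compared to the literature control". The same paragraph expects fusion to be slightly higher at two years than at one. Section 5.12 defines success as a "two year fusion rate comparable to the two and one year fusion rates presented in the literature".

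**Fusion range.** Section 5.12 assumes 88% fusion in 100 patients and adds that "the lower bound of this confidence interval, 81.6%, is within the range of the fusion rates reported in the selected literature". That range is 77% to 97%.

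**The concern.** The safety passage warns against an operation, performs it, and labels the result conservative. For a control failure rate that the device should match, a higher figure is easier to meet. The no-overlap sum is the highest value these five rows allow, so the label points the wrong way for them.

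The fusion passage argues that the device is measured early against literature that is partly late. For the primary endpoint the device is measured at 24 months against literature that is partly at 12. By the protocol's own expectation of slightly higher fusion at two years, the one-year arms then make the benchmark slightly easier, the reverse of a worst case.

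Because *comparable* has no margin, the reader has only these reference figures and their stated justification with which to judge the two components. A reassurance built on the lowest literature arms therefore needs those arms to be named.

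**Working it through.** **Safety**

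Inputs, from the table in 5.2.1 part D: screw loosening 0.4%, rod/plate/screw breakage 1.3%, construct disassembly 0.1%, reoperation/revision 10.9%, neurologic injury 0.8%.

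1. Reproduce the plan: 0.4 + 1.3 + 0.1 + 10.9 + 0.8 = 13.5%, an exact match. Half-width 1.96 × √(0.135 × 0.865 / 100) = 0.0670, the plan's ±6.7%.
2. Bound the share of patients with at least one of the five events. In one population, the largest single rate ≤ share ≤ sum of the rates, so 10.9% ≤ share ≤ 13.5%. The upper end needs no patient to have two of the events; the lower end needs every other event to fall in a reoperated patient. Independence gives 1 − (0.996 × 0.987 × 0.999 × 0.891 × 0.992) = 13.2%.
3. Size: 13.5 − 10.9 = 2.6 points. In 100 patients, 11, 12 or 13 failures would lie above one end and below the other.

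**Fusion average**

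Inputs: counts and time labels in Table 2 (12 arms).

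4. Reproduce the plan: 488/556 = 87.77% (stated 87.79%). Half-width 1.96 × √(0.88 × 0.12 / 100) = 0.0637, so 88 − 6.4 = 81.6%.
5. Split by printed time label. One year: 19/22 + 19/22 + 15/20 + 31/34 = 84/98 = 85.7%. Two years: (488 − 84)/(556 − 98) = 404/458 = 88.2%.
6. Also remove the two-level-only cohort, since the trial treats one level: (404 − 47)/(458 − 61) = 357/397 = 89.9%.

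**Fusion floor against 81.6%**

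Only two arms lie below 81.6%: 47/61 = 77.0% (two-level only, two years) and 15/20 = 75.0% (one year, printed as 77%).

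| Arms kept | Lowest arm | 81.6% inside the range? |
|---|---|---|
| All 12 | 15/20 = 75.0% | Yes |
| Without 47/61 | 15/20 = 75.0% | Yes |
| Without 15/20 | 47/61 = 77.0% | Yes |
| Without all one-year arms | 47/61 = 77.0% | Yes |
| Without both 47/61 and 15/20 | 29/35 = 82.9% (printed 84%) | No |

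Part A says that the study behind the 15/20 arm also reports a two-year rate, but does not give it. Assuming 20 patients again, 16/20 = 80.0% or lower would put 81.6% back inside the range; 17/20 = 85.0% or higher would not.

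**The case against.** **The word *conservative* has a gentler reading.** It may mean restrained compared with adding every row of the table. That is possible, but the text does not say so, and the no-overlap assumption it has just criticised remains in the figure.

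**A reader might infer that the safety comparison as a whole favours the device.** The documents do not support that. The trial's neurological criterion also covers reflex, straight leg raising and tenderness, and section 5.10.3 counts epidural injections, rhizotomies and stimulators among subsequent interventions. The five rows name none of these, which could make 13.5% a strict reference. The net direction is unknown. The 10.9–13.5% bound itself needs a common population, and the unexplained 921 and 814 leave that open.

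**A reader might infer that 81.6% lies outside the relevant literature.** That requires two exclusions at once, and even then depends on the unreported two-year result. Neither arm is wholly unlike the trial: 47/61 matches on interbody fusion and timing, and 15/20 is posterolateral-only, like the roughly 45 patients to be added from the ongoing study (5.13.1).

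**The fusion shift is small and partly disclosed.** This stands. Section 5.12 openly names both one- and two-year rates, and restricting to two-year arms moves the average by only 0.4 points. Part A also notes looser fusion definitions and use of autograft in the literature; both raise published rates and make the benchmark harder. The *assessed at one year* sentence can be defended for the 12-month evaluation in 5.7 and 5.12, but not for the primary endpoint.

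**Some loose ends need sources not supplied.** Examples are whether hardware removal (5.5%) sits inside reoperation/revision, which matters because "Subsequent surgical intervention will be categorized as a revision, removal, reoperation, or supplemental fixation"; the 29/35 arm's time label (marked as a 12-month cohort beside a two-year rate); and Table 3's split by level. These are source checks, not part of this point.

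**Conclusion.** Two justifications are wrong as written, and a third remark needs qualifying.

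- **Safety:** 13.5% is the upper limit for five selected rows, not a conservative control rate. The overstatement from overlap is between 0 and 2.6 points, if the rows share one population. The documents give no overlap data.
- **Fusion time point:** the one-year premise contradicts the 24-month endpoint. The sensitivities are 0.4 points (88.2%) and 2.1 points (89.9%) above 87.8%, taking Table 2's time labels as printed. The 89.9% set still contains multi-level, unstratified and isthmic patients, so it is not a clean single-level benchmark.
- **Fusion range:** the 81.6% remark is true as printed and survives either exclusion alone. It fails only under both, subject to the missing two-year figure.

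Nothing here alters study success: section 5.2 calls the analyses descriptive, and section 5.12 rests success on a 41% composite rate. The correction should be made because section 5.12 judges two components by these figures.

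**What to change.** 1. **5.2.1 part D and 5.12:** remove *conservative*. Present 13.5% as the no-overlap upper limit for the five rows, with the range 10.9–13.5% and the common-population assumption stated. Say what 921 and 814 are. Show the device result against both ends. State that the trial's safety endpoint is wider than these rows, so the net direction of bias is unknown.
2. **5.2.1 part A:** delete the *assessed at one year* sentence or limit it to the 12-month evaluation. Beside 87.79%, report 404/458 = 88.2% and 357/397 = 89.9% as sensitivities only, noting the patient mix that remains and that looser definitions and autograft act the other way.
3. **5.12:** beside the 81.6% remark, name the two arms below it, correct 15/20 to 75.0% or explain the printed 77%, and give the floor with each and both excluded. Add the unreported two-year rate from the source article.

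While the sources are open, check the hardware-removal row, the 29/35 time label and the Table 3 level split.

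The cost is rewording, arithmetic from printed tables and a few look-ups in the cited sources. No new data, visits or patients are needed. The price is a safety range in place of one number and a fusion benchmark shown with slightly higher alternatives.
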